5.7.5.2 Analysis

Quality of Life

A listing of individual responses to the SF-36 questionnaire will be prepared.

For each question of the SF-36 questionnaire, a summary table presenting the raw scores and change from baseline will be generated by dimension, treatment group and measurement time.

Arithmetic means of the global scores will be presented on a histogram by treatment group, with all visits and dimensions on the same graph. Arithmetic means of the

global scores will also be presented on a histogram by dimension, with all visits and treatment group on the same graph.

Individual histograms presenting mean scores by dimension and visit will be produced, with all dimensions on the same graph.

Rescue Medications

A listing of rescue medications will be provided, including the total amount of rescue medication and the time from D1 to first intake of rescue medication.

Summary of count and percentages of subjects having at least one rescue medication will be provided by ATC class and preferred Name, by treatment group.

Summaries of the total amount of rescue medication by preferred Name and the time to first intake (in days) will be provided by treatment group and Placebo group versus all Dysport groups. The number of subjects using a rescue medication and the number of rescue medication taken will also be described by treatment group.

5.8 Safety

5.8.1 *General Consideration*

All safety summaries and analyses will be based upon the Safety population. All safety data will be included in subject data listings (see listing detail conventions in Appendix A5). There will be no statistical comparison between the treatment groups for safety data.

If conversion factors are used, they should be presented either in the relevant section or a link to section 7 should be added.

5.8.2 *Extent of exposure*

In Part B, duration of exposure will be defined in weeks as:
([date of last visit attended – first IMP injection date] +1)/7.

The total dose received will be derived as followed:

- Total Dose (in U) = Number of injection site*Number of units of Dysport received,
- Total dose (in U/cm²) = Total dose / (Total painful area at day 1 pre-dose).

The following extent of exposure summaries will be presented for Part B, by treatment group and all Dysport:

- Summary of the number of injections sites,
- Summary of the volume injected (total and per site),
- Summary of the total dose received by treatment group,
- Summary of the total dose in U/cm² received by treatment group.

The following extent of exposure listings will be presented for Part A and Part B:

- Listing of exposure data (Part B only),
- Listing of subjects receiving test drugs from different batches.

5.8.3 *Adverse Events*

All adverse events (AEs) recorded in the eCRF will be coded using the latest version of MedDRA dictionary in effect within IPSEN at the time of the database lock. AEs will be classified as treatment-emergent AEs (TEAEs) according to the rules below:

- Events with start date and time on or after the date and time of IMP administration in Part B and up to End of Study (EoS) visit or Early Discontinuation (ED).
- Events whose severity worsens on or after the date and time of IMP administration in Part B and up to EoS visit or ED visit,
- Refer to appendix [A3](#) for handling of partial date. In the case where it is not possible to define an AE as treatment emergent or not, the AE will be classified by the worst case; i.e. treatment emergent.

The following summary will be provided by total dose and treatment group (i.e. by injection site dose) and all Dysport for Part B:

- An overview table summarizing the number and percentage of subjects with at least one of the following AEs: any AE; any TEAE; any severe TEAE; treatment-related TEAE; TEAE leading to discontinuation from the study, Serious TEAE, treatment-related Serious TEAE, Serious TEAE leading to death, treatment-related Serious TEAE leading to death, Serious TEAE leading to discontinuation from the study, any Adverse Events of Special Interest (AESI).
The ranges to use for the dose will be precisely defined during the data review meeting.

The following summaries will be provided for Part B by treatment group and all Dysport groups:

- A summary of the number and percentage of subjects reporting a TEAE by treatment group, SOC and PT,
- A summary of the number and percentage of subjects reporting a TEAE by treatment group and PT,
- A summary of the number and percentage of subjects reporting a TEAE by treatment group, causality, SOC and PT,
- A summary of non-serious TEAE by treatment group, SOC and PT.

AEs summaries will be ordered in term of decreasing frequency for SOC and PT within SOC in the treatment group (Part B) and then similarly by decreasing frequency in the treatment group, and then alphabetically for SOC and PT within SOC.

AEs will be counted as follows:

- Subjects with more than one AE within a particular SOC are counted only once for that SOC. Similarly, subjects with more than one AE coding to a particular PT are counted only once for that PT;
- Subjects reporting a TEAE more than once within that SOC/ PT, the TEAE with the worst-case severity will be used in the corresponding severity summaries;

- Subjects reporting a TEAE more than once within that SOC/ PT, the TEAE with the worst-case relationship to study medication will be used in the corresponding relationship summaries;
- If the severity is missing for a TEAE, it will be considered as missing in the summary tables;
- If the causality is missing for a TEAE, it will be considered missing in the summary tables;
- The non-serious TEAEs table should include a specific row “any non-serious TEAE above x%”.

In addition, for each part, a listing with all AEs data will be listed by treatment group including non-TEAEs, Treatment-emergence status will be flagged in the listing, and AESI will also be flagged.

Deaths, Serious Adverse Events, and Other Significant Adverse Events

Adverse events of special interest (AESIs) for IMP Dysport are TEAEs that suggest a possible remote spread of effect of the toxin or events suggestive of hypersensitivity like reactions. TEAEs due to possible remote spread of the effects of IMP Dysport will be identified using the list of MedDRA PTs compatible with the mechanism of action of BTX-A and based on the recommendations from the Committee for Medicinal Products for Human Use (CHMP) and the Food and Drug Administration (FDA). TEAEs potentially representing hypersensitivity reactions will be identified using the Standardised MedDRA Query (SMQ) (narrow search query) for hypersensitivity reactions. A list of MedDRA preferred terms, used to identify any potential AESI, is provided in a separate document AESIs MedDRA version 21.1.xlsx dated 02 April 2019.

All TEAEs identified using the search strategy described above will be medically evaluated during the study, before the database lock and unblinding, by the sponsor to identify events which could possibly represent ‘remote spread of effect of toxin’, or which are suggestive of ‘hypersensitivity reactions’ due to study treatment administration. Cases will be excluded if they are confounded by presence of alternative clinical etiologies (medical history, concomitant medication or diagnosis which could account for the symptoms); if they are considered to be local effects instead of distant spread as judged by the site of injection; the time period between the last study treatment administration and event onset is not in accordance with the expected mechanism of action; or due to insufficient information/evidence to make an assessment.

In the summaries, only the final list of AESIs confirmed by the sponsor as “a possible remote spread event” or “hypersensitivity reactions” will be taken into account.

The following table will be presented:

- AESIs with the number and percentage of subjects and the number of occurrences presented by primary SOC and PT, presented by type of AESI.

The following listings will be provided:

- A listing of all deaths that occurred during the study,
- A listing of all serious adverse events,
- A listing of all adverse events leading to discontinuation of study,

- A listing of subjects having AESIs.

5.8.4 *Laboratory Data*

All laboratory data will be presented in the units of International System of Units (SI).

The following laboratory parameters will be taken at screening:

- **Chemistry:** Albumin, Alkaline Phosphatase (ALP), Alanine Aminotransferase (ALT), Aspartate Aminotransferase (AST), Bicarbonate, Direct Bilirubin, Bilirubin, Calcium, Cholesterol, Creatine Kinase, Chloride, Creatinine, C Reactive Protein, Gamma Glutamyl Transferase (GGT), Glucose, Potassium, Phosphate, Protein, Sodium, Triglycerides, Urea
- **Haematology:** Basophils, Eosinophils, Hematocrit, Hemoglobin, Lymphocytes, Ery. Mean Corpuscular Hemoglobin, Ery. Mean Corpuscular HGB Concentration, Ery. Mean Corpuscular Volume, Monocytes, Neutrophils, Platelets, Erythrocytes, Leukocytes
- **Urinalysis (Qualitative):** Bilirubin, Glucose, Ketones, Nitrite, Occult Blood, pH, Protein, Urobilinogen

In addition, the following listings are to be provided for Part A and Part B:

- Listings of all laboratory data (haematology, clinical chemistry and urinalysis). Out-of-reference-range values will be flagged as high (H) or low (L), or clinically significant (CS). Any unscheduled laboratory assessments will be flagged [U] in the listings.
- Laboratory reference ranges (by gender and age where relevant).

5.8.5 *Vital Signs*

The following Vital signs parameters will be taken in supine position at screening, injection test 1 and 2, baseline, day 1 pre-dose, day 1 post-dose, week 6 and end of study and in standing position at screening only:

- Systolic blood pressure (mmHg),
- Diastolic blood pressure (mmHg),
- Heart rate (beats/min).

The following summaries are to be provided for Part B:

- A summary of the actual and change from baseline (only for supine position) in each vital sign parameter (systolic blood pressure, diastolic blood pressure and heart rate) by treatment group and timepoint,

The following listings are to be provided (Part A and Part B):

- A listing of vital signs data by treatment group, with PCSA values highlighted. PCSA criteria are defined in appendix [A2](#). Any unscheduled vital signs will be flagged [U] in the listing.

5.8.6 *Electrocardiogram (ECG)*

Results from the local ECG, assessed at screening, will be used.

An overall Investigator assessment of ECG will be provided as “normal”, “abnormal, not clinically significant” and “abnormal, clinically significant”. Only investigator assessment and findings (if any) will be recorded in the database.

A summary of the investigator’s interpretation will be provided for Part B. For Part A and Part B, the investigator’s interpretation will be listed with abnormal findings, if any.

5.8.7 *Physical Examination*

Physical examinations include a general inspection, assessed at screening, baseline, day 1 pre-dose, week 6 and end of study and a scar physical examination, assessed at week 6.

Scar physical examination will be coded using the latest version of MedDRA in effect within IPSEN at the time of database lock

The following listings will be provided on Part B:

- A listing of physical examination data,
- A listing of scar physical examination data,
- A listing presenting subjects with at least one physical examination abnormality.

5.8.8 *Pregnancy tests*

Urine pregnancy tests will be performed at screening, at day 1 pre-dose and at end-of-study visit.

A listing with the date of examination, the status of the examination (performed/not performed) and the result (positive/negative) will be provided by treatment group, subject and examination date.

5.9 *Pharmacokinetics (if applicable)*

Not applicable.

5.10 *Anti-drug Antibodies (if applicable)*

Not applicable.

6 *DATA HANDLING*

6.1 *Visit window*

Visits can occur +/- three days around the scheduled date.

6.2 *Unscheduled Visits, Retest, Withdrawal Visit,*

All listings will include retests and unscheduled visits, while for the description by visit in the tables, only the scheduled visits according to the protocol will be described.

Unscheduled visit and retest measurements will be used to provide a measurement for a baseline data or endpoint value (e.g. worst value), if appropriate according to their definition. These measurements will also be used to determine abnormal laboratory, vital signs values or ECG.

If a value requires a retest (for laboratory values, vital signs and ECG) the closest non-missing reliable value to the scheduled visit will be used in the summary tables. An assessment will be considered reliable if it is performed without any technical problem and if the result is within the range of likely values.

Subjects who have withdrawn early from the study have their last assessment entered as visit 90 in the eCRF. By convention, for these subjects, the visit number will be reassigned to the next empty visit number (i.e. if a subject has Visit 1, 2, 3 and 90 entered in the database, the visit number 90 will be reassigned to visit number 4).

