1.8 Known and Potential Risks to Human Subjects

Dysport is licensed in the UK for the symptomatic treatment of focal spasticity, spasmotic torticollis, blepharospasm and hemifacial spasm, injected either intramuscularly or subcutaneously targeting the affected muscles or muscle groups, and is also licensed for treatment of severe primary hyperhidrosis of the axillae, injected intradermally.

Side effects of Dysport as experienced with intradermal injection for hyperhidrosis indication were local injection site reactions including pain, bruising, pruritis, and oedema. In addition, rash and compensatory sweating were also reported.

The maximum licensed intradermal dose is 200 U per area of injections. This maximum recommended intradermal dose will not be exceeded in the present study. Additional information regarding risks to human subjects may be found in the SmPC.

Overall, the safety profile of Dysport is well established after more than 20 years of clinical trials and post-marketing experience in various therapeutic and aesthetic indications at various doses with maximum dose used for intradermal indication up to 200 U at single area of injections. In the current proposed study in subjects with chronic scar pain, we believe the risk associated with Dysport use intradermally, to be acceptable, considering the established and known safety profile with intradermal use.

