7.1.6 Adverse Events of Special Interest

The effects of Dysport and all BTX products may spread from the area of injection to produce symptoms consistent with BTX effects. These symptoms have been reported hours to weeks after injection. Remote spread of toxin that affects swallowing and breathing can be life threatening, and there have been reports of death. The risk of symptoms is increased in subjects who have underlying conditions (e.g. disorders of the neuromuscular junction) that would predispose them to these symptoms. Dysport is contraindicated in individuals with known hypersensitivity to any BTX preparation or to any of the components in the formulation. Adverse events of special interest (AESIs) for Dysport are AEs that suggest a possible remote spread of effect of the toxin or hypersensitivity. A list of preferred terms of AESIs will be provided in the statistical analysis plan (SAP). All AEs will be monitored by the sponsor to determine if they meet the criteria of AESIs. These AESIs will be further analysed to determine if there is a plausible possibility that they represent distant spread of toxin or hypersensitivity. In order to perform the analysis, variables including alternate aetiology (medical history, concomitant medication, or diagnosis which could account for the symptoms), location of Dysport administration, and temporal relationship to Dysport administration will be considered by the sponsor.

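### SAP 5.8.3 puts remote-spread and hypersensitivity candidates through one exclusion list, so a local hypersensitivity reaction could be dropped from the AESI summaries for not being distant spread

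*SAP*

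**What the plan says.** SAP 5.8.3 (Deaths, Serious Adverse Events, and Other Significant Adverse Events) defines AESIs as "TEAEs that suggest a possible remote spread of effect of the toxin or events suggestive of hypersensitivity like reactions". Each type has its own search. Spread candidates come from a "list of MedDRA PTs compatible with the mechanism of action of BTX-A". For the other type, "TEAEs potentially representing hypersensitivity reactions will be identified using the Standardised MedDRA Query (SMQ) (narrow search query) for hypersensitivity reactions".

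The two streams then join: "All TEAEs identified using the search strategy described above will be medically evaluated during the study". The review is done by the sponsor before database lock and unblinding, and its stated aim covers both types. One list of exclusions follows, with four grounds:

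- another clinical explanation;
- a local effect ("if they are considered to be local effects instead of distant spread as judged by the site of injection");
- timing, where the interval from treatment to "event onset is not in accordance with the expected mechanism of action";
- too little information to judge.

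None of the four is restricted to one type. Only sponsor-confirmed events enter the summaries, and the AESI table is split by type.

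Protocol 7.1.6 also covers both types ("AEs that suggest a possible remote spread of effect of the toxin or hypersensitivity"). It names alternative aetiology, location of administration and timing relative to administration as variables for the sponsor to take into account. It does not make location or timing a ground for exclusion.

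**The concern.** The location ground asks whether an event is a local effect or distant spread. That separates true from false candidates for remote spread. It does not do so for hypersensitivity: a reaction to an intradermal injection may be local and still be hypersensitivity. If the ground is applied as worded to a candidate from the hypersensitivity query, the case is excluded because it fails a test for the other AESI type.

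The timing ground raises the same question if the mechanism meant is that of the toxin. Hypersensitivity need not depend on how the toxin acts. Exclusion criterion 2 of the protocol bars people hypersensitive to formulation components such as albumin and lactose, and the placebo contains the Dysport excipients.

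Safety and tolerability is a secondary objective. Because the AESI table is presented by type, a reader will take its hypersensitivity section as the count of confirmed reactions. A confirmation rule that removes local reactions would make that count too low.

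**Working it through.** The point rests on wording, and the documents give no figure to reproduce. The check sets each exclusion ground against the two AESI types.

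| Ground in SAP 5.8.3 | Bears on remote spread? | Bears on hypersensitivity? |
|---|---|---|
| Alternative clinical explanation | Yes | Yes |
| Local effect, not distant spread | Yes | No: a reaction can be local and still be hypersensitivity |
| Onset inconsistent with expected mechanism of action | Yes | Depends on whose mechanism is meant |
| Insufficient information | Yes | Yes |

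**Location.** The contrast with distant spread is in the clause itself. A hypersensitivity reaction confined to the injection site is a local effect and is not distant spread, so it meets the ground as written. Neither document gives hypersensitivity its own location or timing criterion.

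**Timing.** The only mechanism of action named in that part of the SAP is that of BTX-A, where the spread term list is described. Protocol 7.1.6 says that symptoms of spread have been reported from hours to weeks after dosing. Together these make the toxin reading plausible, and on that reading a reaction within minutes would fail the test. The exclusion clause does not name BTX-A, however, so this half is an inference.

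**What one case is worth.** Inputs: 24 subjects planned, blocks of 12, ratio 3:1:3:1:3:1 (Protocol 3.4.1.2; SAP 2.3 and 2.4.2).

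- Subjects per dose: 3 × (24/12) = 6. Pooled Dysport: 3 × 6 = 18.
- One subject removed from a dose arm: 1/6 = 16.7% becomes 0/6 = 0%. Exact 95% intervals: 0.4% to 64.1%, and 0% to 45.9%.
- One subject removed from pooled Dysport: 1/18 = 5.6% becomes 0/18 = 0%. Exact 95% intervals: 0.1% to 27.3%, and 0% to 18.5%.

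Intervals are Clopper-Pearson: lower limit the 2.5% quantile of Beta(x, n − x + 1), upper limit the 97.5% quantile of Beta(x + 1, n − x), with lower limit 0 when x = 0.

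**How often it could arise.** The documents give no rate of search-positive hypersensitivity events. If a fraction p of subjects had one, the chance of at least one among 18 Dysport subjects would be 1 − (1 − p)^18:

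| Assumed p | Chance of at least one in 18 |
|---|---|
| 2% | 30% |
| 5% | 60% |
| 10% | 85% |
| 15% | 95% |

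These are chances that a candidate exists, not that it is local or would be excluded.

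**The case against.** The strongest reply is that the section, read as a whole, does not tell anyone to drop a hypersensitivity case. The review is meant to find hypersensitivity reactions, they are a separate confirmed category, and the table has a place for them. Local as opposed to distant is naturally a question about a spread candidate, and the grounds call for judgement. A sensible medical reviewer could keep a local reaction. This stands: exclusion is what the wording permits, not a certain result. It does not remove the point, because the text sets no limit by type and two reviewers could classify the same event differently.

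Several stronger readings are tempting, but the documents do not support them:

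- *Every local or immediate hypersensitivity reaction is removed.* The location ground leaves room for judgement, and the timing ground can equally be read as the expected timing of the reaction under review, which early onset would fit.
- *The hypersensitivity section could be emptied.* The location ground cannot reach a reaction away from the injection site. Emptying the section needs the contested timing reading, or every case being local.
- *The known local effects of intradermal use would be lost.* Protocol 1.8 lists "local injection site reactions including pain, bruising, pruritis, and oedema", but does not call them hypersensitivity. Whether any would be picked up depends on the narrow query and a separate term file that is not in these documents.
- *Safety data are lost or one arm is favoured.* An excluded event remains in the TEAE tables and the listing of all AEs and, if serious or leading to discontinuation, in its own listing. Review precedes unblinding, so the same rule applies to every arm.

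**Conclusion.** The concern holds as a defect of wording with a limited effect. SAP 5.8.3 states an exclusion ground that, if followed as written, misclassifies a local hypersensitivity reaction. The location ground is the firm part; the timing ground is a problem only if it means the mechanism of BTX-A.

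The harm is possible undercounting of hypersensitivity in the AESI table and the any-AESI overview row, and in the AESI listing as far as it uses the confirmed list. Its size is unknown. The figures of 16.7 and 5.6 percentage points are what any one subject contributes at the planned size, not an estimate of the effect of this rule. They assume 6 and 18 as denominators, which may be larger because some withdrawn subjects are replaced, and they assume that the subject has no other confirmed AESI.

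**What to change.** In SAP 5.8.3, before the blinded medical review:

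- Limit the local-effect ground to candidates from the remote-spread term list.
- Say whose mechanism the timing ground refers to. If it is that of BTX-A, limit this ground in the same way.
- State that injection-site location or early onset alone does not exclude a candidate from the hypersensitivity query.
- Preferably, list all search-positive events with the reason for each exclusion, so that a reader can follow the classification.

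The cost is a short change of wording and, if the last item is adopted, one listing. A few more events may appear in the AESI table. If the sponsor already meant the grounds to apply by type, the edit only records that intention.

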4.4 Safety population

All subjects who received at least one dose of the study drug during the randomised double-blind period (Part B).

For analyses on the safety population, subjects will be classified according to treatment received. If there is any doubt whether a subject was treated or not, he/she will be assumed treated for the purposes of analysis.

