9 APPENDICES

A1. SAS code

Not applicable

A2. Normal ranges

Normal ranges for Vital Signs parameters (Males/Females from 18 to 65 years old):

Parameter	Normal ranges
Systolic Blood Pressure	≤ 95 mmHg ≥ 150 mmHg
Diastolic Blood Pressure	≤ 60 mmHg ≥ 90
Heart Rate	≤ 51 ≥ 100
Body Temperature	≤ 35.5 ≥ 37.5

Normal ranges refer to ranges agreed with the clinical site.

A3.Partial/Missing Date Convention

In all listings, missing or incomplete dates should be left as they have been recorded. However, for calculation / sorting / assignation based on dates, the following methods will be used:

- The most conservative approach will be systematically considered (i.e. if the onset date of an AE/concomitant medication is missing / partial, it is assumed to have occurred during the study treatment phase (i.e. a TEAE for AEs) except if the partial onset date or the stop date indicates differently).
- Where this is possible, the derivations based on a partial date will be presented as superior inequalities (i.e.: for an AE started in FEB2004 after the first IMP administration performed on 31JAN2004, the days since last dose will be “ ≥ 2 ”, similarly the duration of ongoing AEs or medication will be “ $\geq xx$ ” according to the start and last visit dates).

Algorithm for Prior/ Concomitant

Medication, non-drug therapies and surgical procedures start and stop dates will be compared to the date of the first IMP administration to allow classification as either Prior only, Prior and Concomitant, or Concomitant only.

In case of partial start and/or stop medication/ non-drug therapies/surgical procedures dates, imputation will be done to determine the classification:

- If a partial start date, the first day of the month will be imputed for missing day and January for missing month,
- If a partial stop date, the last day of the month will be imputed for missing days and December will be imputed for missing month.

In case incomplete start or stop date does not allow the classification, will be classified as concomitant.

Algorithm for TEAE

For deriving the TEAE flag the following process of temporary date imputation is done (for AE start date only assuming no AE end date are missing). The date imputation algorithm for incomplete adverse event start dates is described in [Table 1](#). Classification of adverse event according to its treatment-emergent status is then done using the imputed date.

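### Candidate AESIs that cannot be assessed are left out of the AESI summaries, so missing information can only lower the reported AESI count

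*SAP*

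**What the plan says.** SAP 5.8.3 defines AESIs as "TEAEs that suggest a possible remote spread of effect of the toxin", or as events suggestive of hypersensitivity. Candidates are found by a preferred-term list for remote spread and a narrow standardised MedDRA query for hypersensitivity. Each candidate is then "medically evaluated during the study, before the database lock and unblinding, by the sponsor".

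Four grounds remove a candidate: an alternative clinical cause, a local rather than distant effect, timing that does not fit the mechanism, or failure to reach a judgement "due to insufficient information/evidence to make an assessment". Reporting then follows the outcome of that review: "In the summaries, only the final list of AESIs confirmed by the sponsor" is used. The outputs named are an AESI table by system organ class and preferred term, an AESI row in the adverse event overview, a flag in the all-AE listing, and a listing of subjects with AESIs. No output is described for candidates that were reviewed and excluded.

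Protocol 7.1.6 also plans a sponsor review. It names three variables to consider: alternate aetiology, location of administration and temporal relationship.

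**The concern.** The first three exclusion grounds rest on evidence against an AESI. The fourth rests on having no evidence either way. A search-positive event that cannot be judged has not been shown to fall short of a possible case, yet it drops out of the table in the same way as an event with a clear alternative cause.

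Safety and tolerability form a secondary objective, and protocol 7.1.6 says that remote spread affecting swallowing or breathing can be life threatening. In arms of about six, a reader is likely to look first at whether the AESI table says none or one. Under this rule, none can mean either that no candidate arose or that a candidate arose and could not be assessed, and the planned AESI outputs do not separate the two.

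Such cases are conceivable. The protocol notes onset from hours to weeks after injection, while its schedule has telephone contact but no planned clinic visit between Day 1 and Week 6.

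**Working it through.** **Planned arm sizes.** SAP 2.4.2 allocates 3:1:3:1:3:1 in blocks of 12, and SAP 2.3 plans about 24 subjects.

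- Each Dysport dose: 24 × 3/12 = 6.
- Each matching placebo: 24 × 1/12 = 2, so pooled placebo = 3 × 2 = 6.
- All Dysport: 3 × 6 = 18. Total: 18 + 6 = 24, which reproduces the SAP's 4 × 6.

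**Direction.** In a group of n subjects, let c be the number with a confirmed AESI, and u the number with an unassessable candidate and no confirmed AESI.

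- Rate under the SAP rule: c/n.
- Rate if unassessable candidates were counted: (c + u)/n.
- Difference: u/n, which is never negative.

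The rule therefore either lowers the count or leaves it alone.

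**Size, for illustration.** Neither document gives an expected number of AESIs or of unassessable cases, so c = 0 with u = 1 or 2 is an assumption. The intervals are exact (Clopper-Pearson) 95% intervals; the SAP does not plan them for this table.

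| Group | SAP rule | One case counted | Two cases counted |
|---|---|---|---|
| One Dysport dose, n = 6 | 0/6 = 0% (0 to 45.9%) | 1/6 = 16.7% (0.4 to 64.1%) | 2/6 = 33.3%, if both are in one arm |
| All Dysport, n = 18 | 0/18 = 0% (0 to 18.5%) | 1/18 = 5.6% (0.1 to 27.3%) | 2/18 = 11.1% |

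**How the SAP treats other safety uncertainty.**

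| What is uncertain | SAP section | Treatment |
|---|---|---|
| Whether an event is treatment emergent | 5.8.3 | Counted in: "the AE will be classified by the worst case; i.e. treatment emergent" |
| Partial or missing onset date | Appendix A3 | Counted in: "The most conservative approach will be systematically considered" |
| Whether the subject was treated | 4.4 | Counted in: "If there is any doubt whether a subject was treated or not, he/she will be assumed treated for the purposes of analysis" |
| Missing severity or causality of a TEAE | 5.8.3 | Shown as missing; the event stays in the table |
| Candidate AESI that cannot be assessed | 5.8.3 | Removed from the AESI summaries |

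Of these five, only the last resolves doubt by removal.

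**Against the protocol.** The first three SAP grounds match the three variables in protocol 7.1.6. The fourth has no counterpart there, and SAP 2.6 does not mention it. Two cautions apply: the protocol's list is open-ended, and SAP 2.6 covers changes to the protocol's statistical section, where 7.1.6 does not sit. The fourth ground is thus an addition to the protocol rather than a contradiction of it.

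**The case against.** A reader might infer more than the documents support, in four ways.

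- **That the SAP breaks its own worst-case rules.** It does not. The Appendix A3 rule concerns handling based on dates, the 5.8.3 rule concerns treatment emergence, and the 4.4 rule concerns exposure. None governs medical adjudication. The nearest analogue, missing severity or causality, is shown as missing and not set to the worst case. What stands is a departure in principle: elsewhere a doubtful event is counted in or kept visible.
- **That the events disappear.** They remain TEAEs, in the tables by system organ class, preferred term and causality and in the all-AE listing. Deaths, serious events and events leading to discontinuation have their own listings, and a life-threatening event meets the protocol's definition of serious. With about 24 subjects, every event can be inspected. The loss is confined to the AESI table and the overview row, and perhaps the AESI flag and listing, whose scope the SAP does not spell out.
- **That the comparison between arms is biased.** The review comes before unblinding, so no bias between arms is expected by design.
- **That the true AESI rate is shown to be understated.** An unassessable case has unknown status. Leaving it out may undercount, and counting it as confirmed may overcount. That is a reason to show such cases separately and not to merge them with the confirmed ones.

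Unassessable cases may also be rare. There is one site, with daily calls to Day 7, two-weekly calls afterwards, and review of continuing events at each assessment. This limits the likely size of the effect but does not change its direction.

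**Conclusion.** The point holds as a reporting weakness in the AESI summaries for both remote spread and hypersensitivity. The rule works in one direction only, and it fits poorly with a definition that asks for no more than a possible case. Each affected subject with no confirmed AESI takes 16.7 percentage points off an arm of six and 5.6 points off the 18 Dysport subjects.

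These figures are the weight of one subject at the planned numbers, not an estimate of what will happen. The total of 24 is approximate, early withdrawals may be replaced, and subjects who were dosed before withdrawing stay in the safety population, so the actual denominators may be somewhat larger. The output shells are a separate document and were not available; if they already display excluded candidates, much of the point is met.

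**What to change.** Amend SAP 5.8.3 before database lock, while the study is still blinded:

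1. Exclude a search-positive event only on positive evidence: an alternative aetiology, a local effect or implausible timing.
2. Put candidates with too little information in a separate row of the AESI table, labelled not assessable / not excluded. The confirmed count stays as it is.
3. Present search-positive and confirmed counts side by side, by treatment group and for all Dysport.
4. List every excluded candidate with the reason for exclusion.

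The cost is a few lines of SAP wording, one table row and one short listing. No new data are needed. The drawback is that the AESI table may look slightly less favourable.
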